## **15.4 Missing Data**

The primary analysis will include all randomized participants analyzed in the treatment group to which they were initially assigned. Thus, a participant who has partial visit data (less than 24 months) may still be included in the primary analyses and it will be critically important to minimize the occurrence of missing data. Obviously, the optimal strategy for dealing with missing data is to make every effort to obtain complete data during the conduct of each RSSP. Our team will work diligently and use a variety of methods to minimize the percentage of missing data in each sub protocol. Nevertheless, there is likely to be a small percentage of missing data. We will employ strategies to mitigate and then assess the impact of missing data within each sub protocol.

To further assess the potential dependence of the results of the primary analysis to these missing values, a series of sensitivity analyses may be conducted as specified within each sub protocol. For participants that do not provide complete data, we will analyze using the following strategies:

- Last Observation Carried Forward: Missing values will be imputed using the participant's last observed data value.
- Multiple Imputation: Two different imputation methods (described below) will be used.
  - Multiple Imputation w/ Treatment-Based Imputation: Under this model, missing data are assumed to follow the same pattern as the respective treatment, age, gender, and baseline value complete data. Missing data will be imputed using a regression approach. If needed, Monte Carlo Markov Chain methodology will be used to impute missing values to obtain a monotone missing data pattern.
  - Pattern-Mixture Model with Placebo-Based Imputation: Under this model, RSSP treatment participants with missing data are assumed to follow the same trajectory as placebo participants. Data from placebo participants only will be used to impute all missing data (from both RSSP treatment and placebo participants) using the full conditional specification regression method.

The results of these analyses will provide valuable information regarding the sensitivity of the findings to the missing data and will be critical in assessing the full value of the RSSP results.

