### **Primary Analyses:**

Both primary endpoints will be tested with equal priority with respect to active treatment superiority versus placebo. Specifically, we maintain a one-sided type I error control of 0.05 for each primary endpoint, not accounting for multiple primary endpoints. Each individual RSSP will meet its pre-specified criteria as a success if either of the endpoints achieves statistical significance.

*Mean Striatum SBR*: For each regimen, a Bayesian repeated measures model of mean striatum SBR over time, adjusted for baseline MDS-UPDRS Part III strata, will be used to compare the slope/progression of active treatment versus the shared concurrent and non-concurrent placebo arm. The model allows for heterogeneity across individual baseline mean striatum SBR values and individual slopes, heterogeneity across regimens due to minor differences in the inclusion/exclusion criteria or mode of administration. A greater negative slope indicates a reduction in the biomarker and a greater progression rate. A hypothesis test for a smaller progression rate for active treatment versus placebo will be conducted using the Bayesian posterior distribution, with a predefined threshold 0.95 required to demonstrate superiority.

*MDS-UPDRS Part III Score*: For each regimen, a Bayesian repeated measures model of MDS-UPDRS Part III score over time, adjusted for the baseline strata, will be used to compare the slope of active treatment versus the shared concurrent and non-concurrent placebo arm. The model allows for heterogeneity across individual baseline MDS-UPDRS Part III score values and individual slopes, heterogeneity across regimens due to minor differences in the inclusion/exclusion criteria or mode of administration. A greater positive slope indicates faster symptom accumulation and a greater progression rate. A hypothesis test for a smaller progression rate for active treatment versus placebo will be conducted using the Bayesian posterior distribution, with a predefined threshold 0.95 required to demonstrate superiority.

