### 5.9 Treatment Duration

Treatment duration for placebo-controlled interventions will be minimum 24 months for each intervention. All participants may remain on the originally assigned treatment arm until the last randomized participant has the opportunity to complete 24 months of follow-up for that specific RSSP or until 24 months since randomization have passed (if terminated early). The RSSP will be closed once all participants have completed the follow-up period. Post-treatment follow-up duration for each intervention will be described in the RSSPs. All participants will be encouraged to continue follow up in the PPMI clinical observational study as per PPMI Schedule of Activities (SOA).

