### 8.2 Randomization

#### 8.2.1 Randomization Procedures

Randomization will be conducted using an interactive response technology (IRT) system embedded within the EDC. The randomization for the Master Protocol consists of a two-stage tiered randomization as described below (see Figure 1).

- 1. In the first stage, participants will initially be assessed according to the Master Protocol inclusion and exclusion criteria. All eligible participants will then be assessed for any additional RSSP specific inclusion and exclusion criteria above that for the Master Protocol that are accessible at the time of screening. Assuming a research participant qualifies for one or more of the ongoing RSSPs, the participant will be randomized equally among all *J* actively enrolling regimens for which they are eligible. Here, regimen denotes both active treatment and placebo groups.
- 2. In the second stage, once assigned to a regimen the participant will then provide informed consent for that specific regimen at their scheduled Regimen-Specific Screening visit. If all additional regimen specific eligibility criteria are met, participants will be stratified by

their baseline MDS-UPDRS part III score ( $<7 \text{ vs.} \ge 7$ ) and randomized in a *J*:1 manner via the IRT system to either the active treatment or placebo for the sub protocol. If the participant screen fails for the assigned regimen (prior to randomization within the regimen), they can be re-randomized to one of the other actively enrolling regimens and complete the required screening procedures. Eligible participants who choose not to consent to their assigned regimen will not be given the opportunity to be re-randomized into an alternative regimen.

The objective of the randomization scheme is to have approximately 1:1 randomization for each active treatment versus concurrently randomized controls.

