# **15.3 Sample Size Considerations**

Overall platform trial sample size is based on the number of regimens. The sample size for each regimen will include 125 participants on active treatment and at least 125 shared concurrent and non-concurrent control participants. To assess the required sample size, analyses were conducted using the observational cohort of participants in PPMI who meet NSD Stage 2B criteria and all eligibility criteria for the Master Protocol (based on a download of the PPMI data from 07/2024). These PPMI participants were recruited in two different cohorts: sporadic PD & prodromal. The participant's enrollment cohort significantly affects progression. Summaries of the two-year decline in the PPMI natural history data by subgroup (PD vs. prodromal) are included in Table 5 below. Assuming that 95% of the randomized participants for the P2P study are expected to come from the < 7 MDS-UPDRS Part III baseline strata, these data were used to inform assumptions for simulating virtual participant outcomes for longitudinal DAT SPECT mean striatum SBR and longitudinal MDS-UPDRS Part III.

Endpoint	PD Cohort (N = 76)	Prodromal Cohort (N = 94)
Mean Striatum SBR	-0.26 (0.17)	-0.12 (0.20)
MDS-UPDRS Part III	6.9 (8.0)	2.9 (3.9)

Table 5: Two-Year Decline in Primary Endpoints by PPMI Natural History Cohort
-------------------------------------------------------------------------------

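### Carrying the last observation forward is listed as a sensitivity analysis for two rate-of-progression endpoints, where it can falsely support or dilute the primary result if dropout differs between arms

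*Protocol*

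**What the plan says.** Section 15.4 keeps every randomized participant, including those with partial data, in the primary analysis. It then turns to sensitivity analyses, and its wording is split: one sentence makes them optional and leaves them to each sub-protocol, while the next commits to three strategies for incomplete data. The first strategy is "Last Observation Carried Forward: Missing values will be imputed using the participant's last observed data value". The others are multiple imputation based on a participant's own treatment group and a pattern-mixture model that imputes from placebo participants. Of the three together, the section says the results "will be critical in assessing the full value of the RSSP results".

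Section 15.1 defines both primary comparisons as differences in rate of change, in mean striatum SBR and in MDS-UPDRS Part III. Section 15.3 gives the natural history in a table titled "Two-Year Decline in Primary Endpoints by PPMI Natural History Cohort": Part III +2.9 (3.9) in the prodromal cohort and +6.9 (8.0) in the PD cohort; SBR −0.12 (0.20) and −0.26 (0.17).

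**The concern.** A carried-forward value is a claim that progression stopped at the last visit. For a slope endpoint in a population that worsens on average, that claim contradicts the protocol's own figures, and Section 15.4 gives no reason for it. Each dropout pulls the slope of their arm towards zero, so unequal dropout becomes an apparent treatment difference.

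A sensitivity analysis exists to show whether the primary result depends on what is assumed about missing data. This one leans towards the arm that loses more participants. If the active arm loses more, it can support a result that is not real. If placebo loses more, it can weaken one that is. Section 15.4 does not say which analysis counts if the three disagree. As this is the master protocol, the text frames every regimen.

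**Working it through.** **Inputs from the protocol.**
- Sample size: "The sample size for each regimen will include 125 participants on active treatment and at least 125 shared concurrent and non-concurrent control participants" (Section 15.3). I use 125 per arm, in line with "The objective of the randomization scheme is to have approximately 1:1 randomization for each active treatment versus concurrently randomized controls" (Section 8.2.1).
- Error rate: "we maintain a one-sided type I error control of 0.05 for each primary endpoint, not accounting for multiple primary endpoints" (Synopsis).
- Follow-up: "Treatment duration for placebo-controlled interventions will be minimum 24 months for each intervention" (Section 5.9). I use 24 months.
- Schedule (Table 1): Part III at months 0, 1, 3, 6, 12, 18 and 24; DAT SPECT at screening, month 12 and month 24.
- Progression: Table 5 prodromal values.

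**Assumptions.** Table 5 entries are mean (SD), progression is linear, and dropout is uniform over 24 months at rates I chose. In the simulations, half of the variance of change lies in the true slopes.

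**Step 1: reproduce Table 6.** Section 15.3 uses "Assuming that 95% of the randomized participants for the P2P study are expected to come from the < 7 MDS-UPDRS Part III baseline strata". Treating that stratum as prodromal (my assumption), a 95/5 mix gives:
- Part III mean 0.95×2.9 + 0.05×6.9 = 3.10; SD √(0.95×3.9² + 0.05×8.0²) = 4.20.
- SBR mean 0.95×0.12 + 0.05×0.26 = 0.127; SD √(0.95×0.20² + 0.05×0.17²) = 0.199.

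At 30% slowing, power for one endpoint is Φ(0.3×mean / (SD×√(2/125)) − 1.645):
- Part III: 0.93/0.531 − 1.645 = 0.11, power 54%.
- SBR: 0.0381/0.0251 − 1.645 = −0.13, power 45%.
- Either endpoint, if independent: 1 − 0.458×0.551 = 75%, against 74% stated.

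All 16 rows of Table 6 are matched within 2 points. With no effect, 1 − 0.95² = 9.75% against the simulated 10.3%. This supports reading Table 5 as mean (SD).

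**Step 2: slope left after carrying forward.** With scans at 0, 12 and 24 months the least-squares slope is (last − first)/24. A participant lost before month 12 carries baseline and keeps none of the slope; one lost later keeps half. The average is 0.5×0 + 0.5×0.5 = 0.25, so an arm with dropout d keeps 1 − 0.75d. The same calculation on the Part III schedule gives 0.41, so that arm keeps 1 − 0.59d.

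If every dropout completes the Early Termination visit (Section 9.12), the value at the time of leaving is carried instead. The kept share per dropout rises to 0.50 for SBR and 0.52 for Part III.

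With no true effect, false slowing = 1 − (share kept, active)/(share kept, placebo):
- SBR, 20% v 10%: 1 − 0.850/0.925 = 8.1%; with the termination visit, 1 − 0.90/0.95 = 5.3%.
- SBR, 30% v 10%: 1 − 0.775/0.925 = 16.2%; with the visit, 1 − 0.85/0.95 = 10.5%.
- Part III, 20% v 10%: 1 − 0.882/0.941 = 6.3%; with the visit, 1 − 0.904/0.952 = 5.0%.
- Part III, 30% v 10%: 1 − 0.823/0.941 = 12.5%; with the visit, 1 − 0.856/0.952 = 10.1%.

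**Step 3: rejections under no effect.** Participants were simulated, values carried forward, individual slopes fitted, and arms compared by a one-sided 5% z-test (3,000 to 8,000 trials per case).

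| Dropout, active v placebo | No termination visit: Part III / SBR | Every dropout has the visit: Part III / SBR |
|---|---|---|
| 10% v 10% | about 5% / 5% | about 5% / 5% |
| 8% v 5% | about 5–7% on both | about 5–7% on both |
| 20% v 10% | about 10–11% / 10% | about 9% / 8% |
| 30% v 10% | about 20% / 19% | about 15–16% / 12–13% |

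**Step 4: the reverse case.** With 20% lost on placebo, 10% on active and a true slowing of 30%, the analysis shows 1 − 0.7×0.941/0.882 = 25% for Part III and 1 − 0.7×0.925/0.850 = 24% for SBR.

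**Step 5: without carrying forward.** Precision-weighted slopes from observed data only, with dropout at random, gave apparent slowing within about 1% and rejections of 4–6% at active dropout of 10%, 20% and 30% against 10% on placebo.

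**The case against.** Much of the case on the other side stands.

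- **The method decides nothing.** Success rests on a posterior probability of at least 0.95 from a repeated measures slope model that already accepts partial data (Section 15.1). A reader might take the rejection rates above as an inflated type I error for the trial. They are not; they belong only to the carried-forward analysis.
- **Its status is not settled.** One sentence makes it optional, and the sub-protocols are not at hand. Treating it as firmly fixed goes beyond the text.
- **It is one of three.** Being listed first does not make it the main one, and the word critical applies to the three results together. The placebo-based model beside it is already a genuine stress test.
- **Stopping drug is not missing data.** Sections 8.3.1 and 8.5.1 encourage off-treatment visits to month 24, Section 8.3.3 allows PPMI data in the intent-to-treat analysis, and Section 9.12 asks for a termination visit. The last of these lowers the figures, most for SBR, but does not remove the bias.
- **The dropout rates are mine.** The protocol expects little missing data. At 8% v 5% the effect is close to nil, and 30% v 10% has no source in the document.
- **Table 5 is thin.** A reader might infer steady worsening in untreated participants. The table gives one two-year change per cohort, with no time course or treatment status.

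None of this gives a reason to keep the analysis. Section 15.4 offers none, and the method is least reliable when dropout differs between arms, which is when a sensitivity analysis is most needed.

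**Conclusion.** The point holds as a weakness in a sensitivity analysis. It is not a flaw in the primary test. Carrying the last value forward assumes no progression after the last visit, against the mean worsening in Table 5, and makes the arm with more missing data look slower to progress.

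Under the stated assumptions and no true effect, 20% v 10% dropout gives about 5–8% false slowing and 8–11% one-sided rejections. At 30% v 10% the figures are about 10–16% and 12–20%. The lower ends assume that every dropout completes the termination visit. Equal dropout with the same timing gives no bias between arms, and small, nearly equal loss gives almost none. The size therefore depends on an imbalance that the protocol neither predicts nor rules out. Importance: minor to moderate. It is worth changing because the change is cheap and reaches every regimen.

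**What to change.** In Section 15.4, delete the carried-forward bullet for the two slope endpoints, or state that its result will not count as support for the primary finding. Keep both imputation analyses. Name the placebo-based pattern-mixture analysis as the stress test and extend it with a delta-adjusted (tipping-point) range, so that readers see how much worse the missing values would have to be to overturn the result. Reconcile the two sentences on status: either these analyses are committed for every regimen, or each sub-protocol chooses them.

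The cost is a few lines of text here and matching text in the SAP and sub-protocols, plus a little programming on top of an imputation already planned. Design, sample size and primary analysis do not change.

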## **15.5 Analysis Populations**

ITT: The primary analysis for each analysis regimen is based on the intent to treat principle and includes all participants randomized to the active treatment arm of the analysis regimen and all

participants in a shared concurrent and non-concurrent control group, regardless of the adherence to the RSSP or duration of follow-up. The analysis shared control group includes all participants randomized to any control arm within any regimen who met the initial eligibility requirements for the specific RSSP of interest at randomization. All data gathered before the regimen's primary analysis date will be included in the regimen's primary analysis unless otherwise agreed upon and noted in the RSSP.

Per-Protocol: To assess the sensitivity of the results, and to obtain knowledge regarding potential effects when the protocol was strictly adhered to, we will also replicate the primary objective using a per protocol population. The PP population includes the subset of all ITT participants who satisfy the following conditions:

- Have satisfactory compliance to assigned treatment, as specified in the RSSP.
- Have no major protocol deviations due to "protocol compliance" (defined as any alteration/modification that has the potential to negatively impact participant safety, integrity of the RSSP, ability to draw conclusions from RSSP data, or affect the participant's willingness to participate in the RSSP)

Only data collected as part of the RSSP will be included in the per-protocol analysis (i.e., no PPMI data will be utilized for participants that drop out of the RSSP but remain in PPMI).

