# **15. STATISTICS**

### **15.1 Primary Endpoints and Analyses**

**Primary scientific question:** Does the treatment slow the rate of progression in DAT SPECT mean striatum SBR or MDS-UPDRS Part III score for those with NSD Stage 2B?

**Primary Endpoints.** To explore this question from the perspective of a biomarker and a clinical measure of symptom worsening, there are two primary endpoints: (a) DAT SPECT mean striatum SBR across time and (b) MDS-UPDRS Part III score across time. Both endpoints are measured until the final participant randomized has the opportunity to complete their 24 month follow up visit in the assigned RSSP. This results in greater than 24 months of follow up on participants randomized earlier in enrollment.

**Primary Analyses.** The Bayesian primary analysis models estimate a difference in the rate of change of each primary endpoint from baseline through last visit, comparing active treatment versus a shared concurrent and non-concurrent placebo. Analyses of treatment superiority will be performed assuming one-sided type I error of 5%. Each primary endpoint will be tested with equal priority with respect to active treatment superiority versus shared concurrent and non-concurrent placebo.

1) DAT SPECT Mean Striatum SBR. A Bayesian repeated measures model of mean striatum SBR, adjusted for baseline MDS-UPDRS part III score strata, will be used to compare the slope of active treatment versus the shared concurrent and non-concurrent placebo arm. The model allows for heterogeneity across individual baseline mean striatum SBR values and individual slopes, heterogeneity across regimens due to minor differences in the inclusion/exclusion criteria or mode of administration.

It is hypothesized that an effective treatment will decrease the progression rate and slow the decline in mean striatum SBR. A greater negative slope indicates a greater reduction in the biomarker and a greater progression rate. The following hypothesis test for a difference in slopes between active treatment and placebo groups will be conducted using the Bayesian posterior distribution.

H0: The active treatment group's average mean striatum SBR slope is equal to or less than that of the shared placebo arm.

 $\mathrm{H}_{a}\!\!:$  The active treatment group's average mean striatum SBR slope is greater than that of the shared placebo arm

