If the Bayesian posterior probability of active treatment superiority  $(H_a)$  is greater than or equal to a prespecified threshold of 0.95, the null hypothesis will be rejected, and the active treatment will be deemed superior to placebo with respect to the mean striatum SBR endpoint. This decision threshold 0.95 has been calibrated to control analysis one-sided type I error at approximately 5% per regimen via simulation.

2) MDS-UPDRS Part III score. A Bayesian repeated measures model of MDS-UPDRS Part III score over time, adjusted for the baseline score strata, will be used to compare the slope of active treatment with the shared concurrent and non-concurrent placebo arm. The model allows for heterogeneity across individual baseline MDS-UPDRS Part III score values and individual slopes, heterogeneity across regimens due to minor differences in the inclusion/exclusion criteria or mode of administration.

It is hypothesized that an effective treatment will decrease the progression rate and slow the increase in symptoms as measured by MDS-UPDRS Part III score. A greater positive slope indicates faster symptom accumulation and a greater progression rate. The following hypothesis test for a difference in slopes between active treatment and placebo groups will be conducted using the Bayesian posterior distribution.

H0: The active treatment group's average MDS-UPDRS Part III slope is equal to or greater than that in the shared placebo arm.

Ha: The active treatment group's average MDS-UPDRS Part III slope is less than that of the shared placebo arm

If the Bayesian posterior probability of active treatment superiority  $(H_a)$  is greater than or equal to a prespecified threshold of 0.95, the null hypothesis will be rejected, and the active treatment will be deemed superior to placebo with respect to the MDS-UPDRS Part III score endpoint. This decision threshold of 0.95 has been calibrated to control analysis one-sided type I error at approximately 5% per regimen with simulation.

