For a specific regimen, "power" is defined as the probability of demonstrating success on at least one of the primary endpoints. The primary analysis population for each regimen includes shared concurrent and non-concurrent control participants. As a result, regimens that enter the platform trial later can be expected to see an increased power relative to that of the first regimen as a result. Assuming 95% of randomized participants within an RSSP fall into the < 7 MDS-UPDRS Part III baseline strata, Table 6 demonstrates the benefits of the stated criteria by showing the probability of success for the first regimen under various assumed true values for the change on each endpoint. The first regimen in the platform is estimated to have 74%, 84%, and 91% power to detect treatment effects when both of the endpoints achieve 30%, 35%, and 40% slowing of progression, respectively. Similarly, we have greater than 86% power to declare success if there is truly a 40% or greater reduction in slope/progression of MDS-UPDRS Part III as long as there is at least a simultaneous 30% or greater reduction in mean striatum SBR. Finally, we have around 83% or higher probability of declaring success if there is truly a 40% or greater reduction in slope/progression on the DAT SPECT imaging endpoint and at least a 30% reduction on slope/progression on the MDS-UPDRS Part III endpoint. The table also demonstrates that the overall type I error probability (probability of meeting the criteria when there is no true reduction for either endpoint) is well controlled at 10.3%. For more details about the operating characteristics for each regimen and the assumptions used to calculate power, refer to the Design Report Appendix in the P2P Statistical Analysis Plan.

UPDRS Slowing	DAT Slowing	Power
0%	0%	10.3%
0%	30%	49%
0%	40%	67%
0%	50%	82%
30%	0%	56%
30%	30%	74%
30%	40%	83%
30%	50%	91%
40%	0%	77%
40%	30%	86%

Table 6: Overall RSSP Power (Win on Either Endpoint)

40%	40%	91%
40%	50%	94%
50%	0%	92%
50%	30%	95%
50%	40%	97%
50%	50%	98%

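### Shared controls need meet only a regimen's initial criteria and may be non-concurrent, and the protocol shows error control only for the first regimen, which has no earlier controls

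*Protocol*

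**What the plan says.** - **Control group (15.5).** The shared control group for a regimen "includes all participants randomized to any control arm within any regimen who met the initial eligibility requirements for the specific RSSP of interest". The sentence ends by setting the time point as randomization. The group explicitly combines concurrent and non-concurrent controls.
- **Active arm (5.5, 8.2.1, 15.2).** Participants are randomised within a regimen only after meeting all of its additional criteria.
- **Screen failures (8.2.1).** "If the participant screen fails for the assigned regimen (prior to randomization within the regimen), they can be re-randomized to one of the other". The rest of that sentence limits this to regimens still open to enrolment.
- **Model (15.1).** The models adjust for baseline Part III strata. For SBR: "The model allows for heterogeneity across individual baseline mean striatum SBR values and individual slopes, heterogeneity across regimens due to minor differences". The protocol traces these to eligibility criteria or mode of administration. The Part III wording is parallel. Randomisation period is not named.
- **Error control (15.1).** "This decision threshold 0.95 has been calibrated to control analysis one-sided type I error at approximately 5% per regimen via simulation".
- **Size and power (15.3).** "The sample size for each regimen will include 125 participants on active treatment and at least 125 shared concurrent and non-concurrent control participants". Table 6 is given for the first regimen, and "regimens that enter the platform trial later can be expected to see an increased power relative to that of the first regimen". Operating characteristics for each regimen are referred to the Design Report Appendix of the SAP.
- **Safety reports (14.8).** DSMB reports compare the intervention with concurrent placebo and regimen-specific controls. No matching efficacy analysis is named.

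**The concern.** Two features can make the shared controls differ from the actives for reasons other than treatment.

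1. **Eligibility.** Actives in regimen B have passed B's initial and additional criteria. A placebo participant in regimen A need only have met B's initial ones. The rule is also unclear for non-concurrent controls: under 5.4 people are screened against active regimens only, so a control randomised before B opened was never screened for B.
2. **Calendar time.** The platform is perpetual, and 15.3 says that enrolment cohort significantly affects progression (two-year SBR change -0.26 in the PD cohort against -0.12 in the prodromal cohort; Part III 6.9 against 2.9). If case mix or progression drifts, earlier controls may have a different placebo slope from the concurrent ones.

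At stake is the per-regimen 5% claim for every regimen after the first. The only tabulated error rate comes from the one setting where borrowing from earlier controls cannot occur.

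**Working it through.** **Inputs.** 125 actives and 125 concurrent controls (15.3; 8.2.1 aims for about 1:1). One-sided 5% per endpoint (15.1). Prodromal two-year change from Table 5: SBR -0.12 (0.20), Part III 2.9 (3.9). I read the brackets as SDs and treat the endpoints as independent.

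**The plan's own figures.** SE = SD × √(2/125): 0.0253 for SBR and 0.493 for Part III.
- 30% slowing: SBR Φ(0.036/0.0253 − 1.645) = 41.2%; Part III Φ(0.87/0.493 − 1.645) = 54.7%. Either: 1 − 0.588 × 0.453 = 73.4% (stated 74%).
- 40% slowing on both: 90.4% (stated 91%).
- Null: 1 − 0.95² = 9.75% (stated 10.3%).

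The approximation is close enough to use below.

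**Eligibility share.** Take two open regimens (J = 2) and let a fraction q of initially eligible people fail B's additional criteria. The documents give no q. Assume that nobody fails A's. Per initially eligible person, A placebo holds 1/2 × 1/3 = 1/6, of whom q/6 would fail B, and B placebo holds (1−q)/6.
- Re-randomised B failures excluded: (q/6) ÷ (1/6 + (1−q)/6) = q/(2−q), that is 5%, 11% and 18% at q = 10%, 20% and 30%.
- Re-randomised B failures counted and allocated at J = 2: they add q/2 × 1/3 = q/6, and the share is q, that is 10%, 20% and 30%.
- Counted but allocated 1:1 (J = 1): they add q/4, giving 12%, 24% and 35%.

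These are shares of B's concurrent controls who would not have qualified for B. They are not estimates of bias.

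**Drift, full pooling.** Take a later regimen with a drug that has no effect, and m = 125 earlier controls progressing faster by d. Bias = d × 125/250. SE = SD × √(1/125 + 1/250) = SD × 0.1095, that is 0.0219 and 0.427. Error = Φ(bias/SE − 1.645). At 20% drift:
- SBR: bias 0.20 × 0.12 × 0.5 = 0.012; Φ(0.548 − 1.645) = 13.6%.
- Part III: bias 0.20 × 2.9 × 0.5 = 0.29; Φ(0.679 − 1.645) = 16.7%.

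**Drift, partial pooling.** Suppose that the regimen term is a random slope with between-regimen SD τ, that earlier controls belong to another regimen, and that concurrent controls share the actives' regimen. With v = SD²/125, the weight on earlier controls is w = v/(2v + 2τ²) and SE² = v(2 − w). Error = Φ(w·d/SE − 1.645). For Part III at τ = 20% of slope: v = 0.1217, w = 0.133, bias 0.133 × 0.58 = 0.077, SE 0.477, error 6.9%.

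| Earlier controls | Pooling | SBR | Part III | Either |
|---|---|---|---|---|
| no drift | full | 5.0% | 5.0% | 9.75% |
| 10% faster | full | 8.5% | 9.6% | 17.3% |
| 20% faster | full | 13.6% | 16.7% | 28.1% |
| 20% faster | τ = 10% of slope | 9.9% | 10.2% | 19.2% |
| 20% faster | τ = 20% of slope | 7.1% | 6.9% | 13.5% |
| 20% faster | τ = 50% of slope | 5.4% | 5.3% | 10.5% |
| 10% slower | full | 2.8% | 2.4% | 5.0% |
| 20% slower | full | 1.4% | 1.0% | 2.4% |

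**A shift built from Table 5.** A PD-cohort share 10 points higher among the earlier controls changes their means by 0.1 × 0.14 = 0.014 and 0.1 × 4.0 = 0.40 (11.7% and 13.8% of the prodromal change). Full pooling then gives 9.3%, 12.0% and 20% for either.

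**Concurrent controls only.** 5.0% per endpoint whatever the drift, with power of about 73% at 30%/30%. Full pooling without drift would give about 83% (m = 125) or 86% (m = 250).

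**The case against.** A reader might infer that the shared controls are not comparable with the actives and that the 5% rate fails for later regimens. The documents do not support either statement.

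- With no drift, pooling keeps 5%. No drift size is documented, and drift in the other direction makes the test conservative at the cost of power.
- Section 15.1 claims about 5% per regimen, and 15.3 sends each regimen's operating characteristics to the SAP appendix, which was not available here. A period term may be in the SAP model, so its absence from the protocol's summary proves nothing.
- The full-pooling figures ignore the regimen-heterogeneity term, which can absorb much of the drift when regimens run at different times.
- The time point at the end of the 15.5 sentence can be read as excluding someone already known to have failed the regimen. Additional criteria may be few, the protocol calls the differences between regimens minor, and nothing ties them to SBR or Part III progression. Some can be assessed only after regimen-specific consent, which is a practical reason for using initial criteria.
- Section 5.2 adopts the combined control group deliberately. The 1:1 aim in 8.2.1 describes allocation and does not define the analysis set.

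All of this limits the claim. What remains: even on the narrow reading, other regimens' controls are not tested on the additional criteria, and the rule is fixed in the protocol. The regimen term also offers no free protection, because it absorbs drift by borrowing less, and the promised power gain shrinks with it.

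**Conclusion.** The point holds in limited form. The protocol fixes a primary control rule wider than the active arm's eligibility, leaves the status of re-randomised screen failures open to a literal reading that includes them, and puts non-concurrent controls into the primary analysis without a concurrent-only efficacy result. Error control is tabulated only for the first regimen, so 5% for later regimens is asserted and not shown.

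The possible size runs from no inflation to 13.6% (SBR) and 16.7% (Part III) at 20% drift under full pooling, or about 5-10% per endpoint with partial absorption. These figures rest on an assumed drift, 125 earlier controls, Table 5 brackets read as SDs, and concurrent controls in the same regimen as the actives. The either-endpoint figures also assume independence. The ineligible share is 5-18% on the narrow reading for q of 10-30%, and its effect on the treatment comparison is unknown. The stated 74% power is not in question. The change is worth making because drift is plausible on the protocol's own data and the remedy is cheap.

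**What to change.** 1. In 15.5, restrict a regimen's shared controls to those who meet all of its criteria, initial and additional, that can be evaluated from Master Protocol or PPMI data. Exclude anyone who screen-failed that regimen. State how the rule applies to controls randomised before the regimen opened.
2. In 15.1 or 15.5, report a concurrent-control-only analysis of both primary endpoints beside the primary result.
3. Confirm that the SAP model handles randomisation period, and that the per-regimen 5% claim was simulated for a later regimen under drift. If it was not, limit the claim to the first regimen until that is done.

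**Cost.** Wording, slightly fewer shared controls and one added analysis, plus a simulation run if none exists for a later regimen under drift. The primary analysis may still borrow non-concurrent controls. The concurrent-only result has about first-regimen power (73% at 30%/30% by the approximation above).
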